10.3.5 Transfusion Independence Rates

Post baseline transfusion independence rate will be calculated as the proportion of subjects who achieved transfusion independence post baseline. Transfusion independence is defined as a period of at least 56 days (≥ 56 days) with no transfusion after the first dose of study drug and on or before the last dose of study drug + 30 days or before death or before the initiation of post-treatment therapy, whichever is earlier. In addition, the rate of conversion will be calculated as proportion of subjects being post-baseline transfusion independent from baseline transfusion dependence. The transfusion independence rate will be evaluated for 1) RBC and 2) platelets. All subjects in the full analysis set will be included in the analysis. Subjects who did not receive any study drug are considered as transfusion dependent.

The post-baseline transfusion independence rates will be compared between two arms using CMH test stratified by AML status (de novo, secondary) and age ($18 - < 75, \geq 75$). In addition, 95% confidence interval based on the binomial distribution (Clopper-Pearson exact method) by treatment arms will be provided for the post-baseline transfusion independence rate. The risk difference and 95% confidence interval for the risk difference (exact unconditional confidence limits) will also be provided.

The rates of conversion from baseline transfusion dependence to post-baseline transfusion independence for 1) RBC and 2) platelets will be estimated and the 95% confidence interval based on the binomial distribution (Clopper-Pearson exact method) by treatment arms will be provided. The risk difference and 95% confidence interval for the risk difference (exact unconditional confidence limits) will also be provided.

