EFS will be defined as the number of days from randomization to the date of progressive disease, relapse from CR to CRi, treatment failure defined as failure to achieve CR, CRi, PR, or MFLS, or death from any cause. If a specified event does not occur, subjects will be censored at the date of last disease assessment. Data for subjects without any disease assessments performed after randomization will be censored at the date of randomization. The distribution of EFS will be estimated for each treatment arm using Kaplan-Meier methodology and compared between treatment arms using the log-rank test stratified by AML status (secondary, de novo) and age ($18 - < 75, \geq 75$).

Post baseline transfusion independence rate will be calculated as the portion of subjects who achieved transfusion independence post baseline. Transfusion independence is defined as a period of at least 56 days with no transfusion between the first dose of study drug and the last dose of study drug plus 30 days. In addition, the rate of conversion will be calculated as proportion of subjects being post-baseline transfusion independent from baseline transfusion dependence. The transfusion independence rate will be evaluated for 1) RBC and 2) platelets. All randomized subjects will be included to estimate the post-baseline transfusion independence rate.

Post baseline transfusion independence rate will be estimated as the proportion of subjects known to achieve transfusion independence during the evaluation period. Transfusion independence rate will be compared between treatment arms using CMH test stratified by AML status (secondary, de novo) and age ($18 - < 75, \geq 75$). In addition, 95% confidence interval will be constructed for transfusion independence rate.

The rates of conversion from baseline transfusion dependence to post-baseline transfusion independence will be estimated. The conversion rate will be evaluated for 1) RBC and 2) platelets.

The proportion of subjects with complete remission or complete remission with partial hematologic recovery (CR + CRh) by the initiation of Cycle 2 will be calculated. CR + CRh rate by the initiation of Cycle 2 will be compared between treatment arms using CMH test stratified by AML status (secondary, de novo) and age ($18 < 75, \geq 75$). In addition, 95% confidence interval will be constructed for CR + CRh rate by the initiation of Cycle 2.

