6.0 Analysis Conventions

General Considerations

Unless otherwise noted, for all statistical analyses, statistical significance will be determined by a two-sided P value ≤ 0.05 . The date of randomization is defined as the date that the IVRS/IWRS issues a randomization number.

Definition of Study Drug

Unless otherwise specified, the study drug in this document refers to venetoclax/placebo and LDAC. The first dose date of study drug is defined as the date the 1st dose of venetoclax/placebo or LDAC, whichever occurs first, is administered. The last dose date of study drug is defined as the date the last dose of venetoclax/placebo or LDAC, whichever occurs later, is administered.

Definition of Baseline

All baseline summary statistics and analyses will be based on characteristics prior to the initiation of any component of study drug (or randomization for non-treated subjects). Unless otherwise stated, baseline for a given variable will be defined as the last value for that variable obtained prior to the first dose of any component of study drug or randomization for non-treated subjects.

Definition of Final Observation

The final observation in [Table 2](#) and [Table 3](#) is defined as the last non-missing observation collected after the first dose of study drug to the last dose of study drug + 30 days.

Definition of Data Cutoff Date

The data cutoff date for interim analysis (IA) will be the projected date of the 100th death occurred in the full analysis set. The data cutoff date for final analysis (FA) will be the projected date of the 133th death occurred in the full analysis set.

The same data cutoff date will be implemented for both efficacy and safety analyses.

Stratification Factor for Efficacy Analyses

AML status (secondary, de novo) and age ($18 < 75, \geq 75$) will be used in all stratified analyses of the efficacy endpoints. The stratification factor value under which the subject is randomized by the IVRS/IWRS will be used in the efficacy analyses.

Definition of Cycle Rx Days in Each Cycle

Cycle Rx Days for each cycle are calculated for each time point relative to first dose of study drug in each cycle. The day of the first dose of study drug in each cycle is defined as Cycle Rx Day 1, while the day prior to the first dose of study drug is defined as Cycle Rx Day -1 (there is no Cycle Rx Day 0).

Definition of Analysis Windows

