10.0 Efficacy Analysis

10.1 General Considerations

Unless otherwise noted, for all statistical analysis, statistical significance will be determined by a two-sided P value ≤ 0.05 (when rounded to three decimal places).

When the 133st death in the full analysis set occurs, there will be a final review of the eCRF data. After the data collection is completed and reviewed for completeness and all data management quality assurance (QA) and quality control (QC) procedures are performed, the study blind will be broken and clinical database data will be extracted for documentation and statistical analyses of the efficacy and safety data. Efficacy analyses will be performed on the full analysis set.

Unless otherwise specified, the primary analysis of all response/progression related endpoints (e.g., CR/CRi) will be based on the investigator assessment. Sensitivity analyses will be performed based on Independent Review Committee's assessment.

For the analysis of all response/progression related endpoints, MRD response rate, and transfusion independence rate, the data collected after the data cutoff date or initiation of post treatment therapy, whichever comes earlier, will be excluded.

Censoring Dates for Prematurely Blind Broken Subjects

For all efficacy endpoints except OS, if the subject's blind has prematurely broken by sites before "Cutoff" date, the date of premature blind break will be set as "Cutoff" date for the subject.

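### The transfusion-independence window in SAP 10.3.5 does not end at the data cutoff, so read literally it can credit up to 30 unobserved days as transfusion-free

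*SAP*

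**What the plan says.** - **Window, SAP 10.3.5.** "Transfusion independence is defined as a period of at least 56 days (≥ 56 days) with no transfusion after the first dose of study drug". It must end on or before "the last dose of study drug + 30 days or before death or before the initiation of post-treatment therapy, whichever is earlier". Three end points are listed, and the data cutoff is not among them.
- **Window, Protocol 8.1.4.2.** The period is "at least 56 days with no transfusion between the first dose of study drug and the last dose of study drug" plus 30 days, again with no cutoff. The same section estimates the rate from subjects who are known to have reached independence in the evaluation period. SAP 10.3.5 does not repeat that qualifier.
- **Cutoff, SAP 10.1.** The general exclusion rule names this endpoint: "transfusion independence rate, the data collected after the data cutoff date or initiation of post treatment therapy, whichever comes earlier, will be excluded". For a subject whose blind is broken early by the site, the cutoff for all efficacy endpoints except OS becomes the date of the break.
- **Last dose, SAP 6.0.** "The last dose date of study drug is defined as the date the last dose of venetoclax/placebo or LDAC, whichever occurs later, is administered". Nothing is said about subjects who are still on treatment at the cutoff.
- **Rank, SAP 10.7.** Platelet independence is third in the EU sequence and fourth in the US sequence. RBC independence is seventh and eighth.

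**The concern.** For a remission endpoint, dropping data after the cutoff can only remove evidence of success. For transfusion independence it can create success, because a day without a transfusion record looks like a transfusion-free day. SAP 10.1 removes the records and SAP 10.3.5 sets the window, and no rule shortens the window to match. A programmer who follows SAP 10.3.5 as written would compute last dose + 30 days for everyone, including a subject dosed on the cutoff day.

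The endpoint stands high in a fixed sequence, so a borderline platelet result decides whether everything ranked below it can be tested. The analyses without a cutoff in SAP 10.6 do not include this endpoint, so no planned sensitivity analysis would show the effect.

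**Working it through.** **No plan figure to reproduce.** The documents give no rate, power or sample size for transfusion independence. The stated design figures (133 deaths, 90% power) concern OS only. They do reproduce, with 90.4% power at 133 deaths allowing for the interim look, but they do not bear on this point. Only the timing of the cutoffs, at the 100th and 133rd deaths, is used below.

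**1. Window arithmetic** (inputs from SAP 10.3.5: 56 days and 30 days). Let g be the days from last dose to cutoff. Then overrun = max(0, 30 − g), and observed days needed = 56 − overrun.

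| g (days) | Overrun (days) | Observed days needed |
|---|---|---|
| 0 | 30 | 26 |
| 7 | 23 | 33 |
| 14 | 16 | 40 |
| 30 | 0 | 56 |

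At g = 0, 30/56 = 54% of the qualifying period is unobserved. With the window cut at the cutoff, the overrun is 0 and all 56 days must be observed.

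**2. Who can change status.** Only a subject with no other 56-day period, who has about 26 to 55 transfusion-free days running up to the cutoff. If all 210 are randomized by then, at most 210 − 100 = 110 subjects are alive at the interim and 210 − 133 = 77 at the final analysis. The documents do not say how many would be on treatment.

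**3. Per-subject effect (assumed transfusion process).** Transfusions occur at random at a constant rate, and the longest gap in [0, L] is compared with the longest gap in [0, L + 30] with the last 30 days empty. For L = 120 days and one transfusion per 14 days on average, the chance of being called independent rises from 10% to 23%, or 13 points. Over L = 60 to 300 days and one transfusion per 14 to 28 days, the rise is roughly 5 to 27 points.

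**4. Share on treatment at the cutoff (assumed).** Inputs are exponential OS with the plan's medians (11 v 6 months), assumed median treatment of 4.5 v 2.5 months, and assumed accrual of 12 to 24 months. The shares are about 20–23% v 7–12% at the interim and 7–11% v 1–4% at the final analysis.

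**5. Effect on the difference between arms.** Simulating steps 3 and 4 together, with each on-treatment subject's own exposure at the cutoff, gives about 1.1 to 1.6 points at the interim and 0.3 to 0.8 at the final analysis. As a rough check, multiply the difference in shares by 13 points:
- Interim: (0.20 − 0.07) × 13 = 1.7 and (0.23 − 0.12) × 13 = 1.4.
- Final: (0.07 − 0.01) × 13 = 0.8 and (0.11 − 0.04) × 13 = 0.9.

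The simulated values are somewhat lower, most clearly at the final analysis, where subjects still treated have long exposure and gain less.

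**6. What this could do to a test (assumed rates, unstratified z-test, one-sided p).** Start from 35/140 v 10/70, a difference of 10.7 points with p = 0.037.
- Three extra responders on venetoclax and one on placebo: 38/140 v 11/70, 11.4 points, p = 0.033. This shift of 0.7 points is within the final-analysis range.
- Three extra on venetoclax only: 38/140 v 10/70, 12.9 points, p = 0.018. This shift of 3/140 = 2.1 points is larger than step 5 supports.

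**The case against.** The strongest reply is that the SAP already applies the cutoff to this endpoint by name. SAP 10.1 treats the cutoff and post-treatment therapy as a pair, and SAP 10.3.5 makes therapy a window end, so the natural joint reading is that evaluation stops at the cutoff too. The subject-level rule sits under a heading about censoring dates, which also treats the cutoff as an end of observation. A subject with 26 observed and 30 unobserved days is not known to have reached 56, as the protocol requires.

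This stands as evidence of intent. A reader might infer that the plan instructs post-cutoff days to be counted as transfusion-free. No sentence says so. But the list in SAP 10.3.5 is closed by its whichever-is-earlier clause, and it repeats therapy from SAP 10.1 while leaving out the cutoff. By contrast, OS (10.2.1), response by Cycle 2 (10.3.3), EFS (Table 4) and duration of response (Table 5) all name the cutoff in their own rules. The intended reading is probable but not written.

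Three further inferences go too far:
- **That nothing is collected once a subject stops treatment.** Protocol 5.1.4 provides a safety visit about 30 days after discontinuation, and Protocol 6.1.4 collects adverse events over that time. Only subjects who leave all follow-up are affected.
- **That the per-subject rise in step 3 is the size of the bias.** It applies only to subjects on treatment and still being transfused. CR itself requires red-cell transfusion independence, so long-treated subjects are likely to include many who already qualify and cannot change status. If half are still transfused, the figures in step 5 halve.
- **That the bias certainly favours venetoclax.** The documents give no on-treatment shares by arm. With the same assumed discontinuation rate in both arms (median 3.5 months), the planned OS medians still leave more venetoclax subjects on treatment, but by less: 15–18% v 11–15% at the interim and 4–8% v 3–6% at the final analysis.

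**Conclusion.** The point holds as a gap between two stated rules, not as a miscount that the plan prescribes. SAP 10.3.5 omits the cutoff from the window, SAP 10.1 only excludes the data, and applied literally the two can credit up to 30 unobserved days. Subjects last dosed within 30 days before the cutoff are affected in part. For a prematurely unblinded subject who keeps dosing, the overrun could exceed 30 days if the last dose is not also limited to the subject-level cutoff.

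The probable size is small: about 1.1 to 1.6 points at the interim and 0.3 to 0.8 at the final analysis. These figures rest on assumed treatment durations, accrual and a constant transfusion rate, none of which the documents give, and on the window not being truncated. The primary endpoint is untouched. The point matters only for a near-boundary transfusion result, and through it for the endpoints ranked below.

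**What to change.** In SAP 10.3.5, end the evaluation window at the earliest of:
- last dose + 30 days
- death
- start of post-treatment therapy
- the data cutoff, or the subject-level cutoff after premature unblinding
- for subjects who withdraw from all follow-up, the last date with transfusion information.

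State that all 56 days must lie inside this window, and check that the programmed derivation does the same. The cost is one sentence and a line of code. The rates may come out slightly lower, since a few subjects with short observed periods at the cutoff would no longer count as independent.

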5.3.1.1 Study Procedures

All study procedures outlined in [Appendix C](#) are discussed in detail in this section, with the exception of adverse event information (discussed in Section 6.0). All study data will be recorded on eCRFs.

Procedures performed at Screening will serve as baseline, unless repeated on Cycle 1 Day 1 prior to dosing; in which case the latter will serve as baseline. Any abnormal laboratory or vital sign assessment between screening and prior to administration of study drug will be recorded in the subject's medical history and will also serve as the subject's baseline. The highest grade of cytopenias will be recorded in the subject's medical history, including any transfusion support and prophylaxis received, regardless if screening value indicates a lesser grade.

A subject who has signed the informed consent, has had at least one study procedure conducted, and is determined to be a screen failure, will not proceed into the study. Rescreening may be performed upon investigator discussion with the AbbVie Medical Monitor and subsequent agreement.

Informed Consent

Signed informed consent form will be obtained from the subject or the subject's legally acceptable representative in order to participate in this study. The IRB approved informed consent form must be signed and dated by each subject prior to undergoing any study procedures or before any prohibited medications are withheld from the subject in order to participate in this study. Informed consent will also be required for the optional exploratory research sampling portion of the study. Refer to Section 9.3 for details on obtaining and documenting informed consents.

Medical and Oncologic History

The following will be collected during the Screening Visit:

- Complete medical history, including documentation of any clinically significant medical conditions
- History of tobacco and alcohol use
- Detailed oncology history including:
 - Date of diagnosis of AML and subtype
 - Date of diagnosis of any previous malignancy and/or antecedent hematologic disorder
 - Histology
 - Any surgical procedures
 - Treatments administered (including dates and type of modality)
 - Transfusion of blood products within 8 weeks
- Prior and concomitant medication usage including dates of usage and dosing information for all medications and supplements taken.

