5.2 Variables Used for Stratification of Randomization

The subject randomization will be stratified by AML status (de novo, secondary), age (18 – < 75, ≥ 75), and region (US, EU, China, Japan (JP), Rest of World (ROW)).

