8.2 Demographic and Baseline Characteristics

All baseline characteristic summary statistics and analyses are based on characteristics prior to the first dose of study drug or date of randomization for non-treated subjects.

Distributions of the continuous demographic and baseline characteristic variables will be summarized by treatment arm with the number of non-missing observations, mean, standard deviation, and median, as well as the minimum and maximum values.

For the categorical demographic and baseline characteristic variables, the frequency and percentages of subjects within each category will be summarized by treatment arm. The number of subjects with missing information will also be summarized.

There will be no statistical comparison for the demographic and baseline characteristics between the two treatment arms.

The following demographic and baseline characteristics will be summarized:

Demographics:

- age (years) and age categories (18 – < 75 years, ≥ 75 years)
- gender (male/female)
- race (white, black or African American, Asian, and other)
- region (US, EU, China, JP, and ROW)
- height (cm)

- weight (kg)

Baseline and Disease-Related Characteristics:

- ECOG performance status (0, 1, 2, 3)
- AML Status (de novo, secondary)
- Type of secondary AML (therapy related, post MDS/CMML)
- AML with myelodysplasia related changes (AML-MRC) (Yes, No)
- Cytogenetics risk (favorable, intermediate, poor)
- Bone marrow blast count (< 30%, ≥ 30% – < 50%, ≥ 50%)
- Bone marrow blast count (%)
- CTC grade of neutropenia
- Neutrophils value ($\times 10^9/L$)
- CTC grade of anemia
- Hemoglobin value (G/L)
- CTC grade of thrombocytopenia
- Platelet count ($\times 10^9/L$)
- Reasons for being not eligible for standard induction therapy
- Prior HMA used (Yes, No)
- Antecedent hematologic history of MDS (Yes, No)
- Baseline RBC transfusion dependence (Yes, No)
- Baseline platelet transfusion dependence (Yes, No)
- Molecular marker via central lab (FLT3, IDH1/2, TP53, NPM1)
- Hepatic impairment (Yes, No)
- Renal impairment (Yes, No)

The cross tabulation of the following demographic and baseline characteristics captured in IVRS/IWRS and CRF will be generated:

- Age categories (18 – < 75, ≥ 75 years)
- AML status (de novo, secondary)

- Cytogenetics risk (favorable, intermediate, poor)
- Region (US, EU, China, JP, and ROW)

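### Post-baseline platelet and RBC transfusion independence are tested without adjusting for baseline dependence on the same product: a valid test, but one that gives up some power and leaves chance imbalance uncorrected

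*SAP*

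**What the plan says.** **The test.** SAP 10.3.5: "The post-baseline transfusion independence rates will be compared between two arms using CMH test stratified by AML status (de novo, secondary) and age". Protocol 8.1.4.2 agrees: "Transfusion independence rate will be compared between treatment arms using CMH test stratified by" the same two factors. SAP 6.0 makes this a general rule, saying of AML status and age that they "will be used in all stratified analyses of the efficacy endpoints".

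**The endpoint.** SAP 10.3.5: "Transfusion independence is defined as a period of at least 56 days (≥ 56 days) with no transfusion after the first dose of study drug", ending at the earliest of last dose plus 30 days, death or post-treatment therapy. The whole full analysis set counts, and untreated subjects are classed as dependent.

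**The baseline variable.** SAP 8.2 lists "Baseline platelet transfusion dependence (Yes, No" among the characteristics to be tabulated, with a matching item for RBC. Screening history in Protocol 5.3.1.1 includes "Transfusion of blood products within 8 weeks", and SAP 8.4 summarises pre-dose transfusions by type. Neither document defines baseline dependence or its look-back window.

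**Balance.** SAP 5.2: "The subject randomization will be stratified by AML status (de novo, secondary), age" and region. Transfusion dependence is not a factor.

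**Where baseline dependence is used.** SAP 10.3.5 estimates conversion from dependence to independence for each product, with intervals per arm and a between-arm risk difference with interval. It gives these no test, and Tables 7 and 8 give them no rank. Baseline dependence does not appear in SAP 10.6 or in the open-ended subgroup list of SAP 10.8.

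**Rank.** Platelet independence is 3rd of 14 (Table 7, EU) and 4th of 16 (Table 8, US). RBC independence is 7th and 8th.

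**The concern.** Subjects who need transfusions at entry and subjects who do not may well have different chances of a 56-day transfusion-free period on treatment. If so, baseline dependence is a prognostic covariate closely tied to the outcome, and leaving it out has two effects. Outcome variance that the covariate would explain stays in the test statistic and lowers power. A chance difference between the arms in baseline dependence also passes into the rate difference, and the planned risk difference is not described as stratified.

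The rank adds some weight. In a fixed sequence, a miss on platelet independence stops formal claims on the 14 − 3 = 11 endpoints below it in the EU order, or the 16 − 4 = 12 below it in the US order.

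**Working it through.** **1. The plan's own figure.** The documents state power for OS only. With HR 0.545, 2:1 allocation, two-sided 0.05 and 90% power, the Schoenfeld formula gives (1.960 + 1.282)² / [(2/9)(ln 0.545)²] = 129 deaths. With a Lan-DeMets O'Brien-Fleming look at 75% the requirement is 131, and power at 133 is 90.5%. The one-sided boundaries come out at 0.0097 and 0.0221, against 0.010 and 0.022 in SAP Table 1. The OS design reproduces. No stated power exists to reproduce for the transfusion endpoints.

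**2. Inputs.** From the documents: 140 v 70 subjects, CMH test, two-sided 0.05. Assumed, because the documents are silent: share dependent at baseline (π) 35% to 75%; control-arm independence rates p_i (baseline independent) of 30% to 50% and p_d (baseline dependent) of 10% to 20%; common odds ratio 2.5; AML-by-age strata holding 24%, 16%, 36% and 24% of subjects, with no effect of their own.

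**3. Variance explained.** With p = π·p_d + (1 − π)·p_i,

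R² = 1 − [π·p_d(1 − p_d) + (1 − π)·p_i(1 − p_i)] / [p(1 − p)],

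and the equivalent sample-size gain is 1/(1 − R²) − 1. Example with π = 0.5, p_i = 0.45, p_d = 0.15: p = 0.30, R² = 1 − (0.06375 + 0.12375)/0.21 = 0.107, gain 12.0%.

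**4. Power.** CMH with the 4 planned strata v 8 strata (dependence added), simulated with 8,000 trials per row (Monte Carlo SE about 0.5 points):

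| Dependent at baseline | p_i / p_d | R² | Sample-size equivalent | Planned | With stratum | Gain (points) |
|---|---|---|---|---|---|---|
| 50% | 30% / 20% | 1.3% | 1.4% | 81.7% | 81.5% | −0.2 |
| 35% | 40% / 15% | 6.6% | 7.1% | 78.9% | 82.0% | 3.1 |
| 75% | 40% / 15% | 7.0% | 7.5% | 72.1% | 74.6% | 2.5 |
| 50% | 45% / 15% | 10.7% | 12.0% | 74.2% | 79.0% | 4.8 |
| 50% | 50% / 10% | 19.0% | 23.5% | 63.5% | 73.3% | 9.8 |

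The gain shrinks when power is already high. With 40% dependent and a log odds ratio of 1.3, rates of 45% / 25% give 98.8% v 98.9%, and 55% / 15% give 94.6% v 97.1%. It stays large only for an extreme split: 60% / 10% gives 86.0% v 94.8%.

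**5. Type I error.** Under the null, rejection was 5.0% to 5.4% as planned and 4.8% to 5.4% with the added stratum. Both tests hold their level.

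**6. Chance imbalance.** Treating dependence as unrelated to the randomisation factors, the SD of the between-arm difference is √[π(1 − π)(1/140 + 1/70)]. For π = 0.5 this is 0.073, so the 95% range is ±14.3 points; for π = 0.75 it is ±12.4. In the simulations the arms differed by 10 points or more in about 11% to 18% of trials. The shift in the crude risk difference is imbalance × (p_i − p_d). At 10 points it runs from 0.10 × 0.10 = 1.0 point to 0.10 × 0.40 = 4.0 points. At the edge of the 95% range it runs from 1.4 to 5.7 points.

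In null trials where the venetoclax arm had at least 10 points less baseline dependence, the planned test rejected in 5.3% to 6.4% of trials in the first four rows of the table and 12.5% in the last. The adjusted test rejected in 4.8% to 5.6%. These subsets are small (roughly 440 to 710 trials, SE 1 point or more), so only the last row clearly shows an excess. A repeat of that row with 20,000 trials gave 9.5%.

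**The case against.** The strongest reply is that nothing is wrong. The test holds its level, chance imbalance is already allowed for in an unconditional p-value, and using the same two randomisation factors for every efficacy test is a consistent, pre-specified rule. All of that stands. A reader might infer that the analysis is biased or invalid, but neither the documents nor the null simulations support that.

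A reader might also infer that the plan ignores baseline dependence. It does not. The conversion analysis gives a between-arm risk difference with a confidence interval among baseline-dependent subjects, and tabulation by arm will show any imbalance. What remains is that these do not adjust the ranked test.

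The predictive strength is also uncertain. Any qualifying 56-day period counts, so a subject transfused early can still succeed, and one who needs no transfusion at entry fails if death or discontinuation comes early. With an assumed control median OS of 6 months (SAP 4.3), survival and time on drug may matter as much as baseline status. Nor is it settled that the baseline variable covers the same 56 days as the endpoint: the 8-week history makes that natural, but no definition says so.

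Finally, a generic correlation of 0.5 would suggest a rise from 80% to 90%: Φ[(1.960 + 0.842)/√0.75 − 1.960] = 0.90. No passage supports that value, and the five tabulated scenarios correspond to correlations of only about 0.11 to 0.44 (√R²). It should not be used.

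**Conclusion.** The point holds as a cheap improvement. Two ranked endpoints are tested without a baseline covariate that the trial already collects and that is closely tied to the outcome. The consequence is lost efficiency and exposure to chance imbalance, with overall type I error intact.

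The gain from adjusting is about 0 to 10 power points, typically 2 to 5. It is close to zero if baseline dependence predicts weakly or if power is already high. These figures rest on assumed dependence rates, control rates and odds ratios, because the documents give none.

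A reader might infer that the platelet test is likely to fail and block the endpoints below it. The sequence does work that way after a miss, but no planned power is stated for this endpoint, so the documents do not show that a miss is likely.

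**What to change.** Before unblinding, amend SAP 10.3.5, with a matching exception in SAP 6.0 and alignment of Protocol 8.1.4.2:

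- Stratify the platelet test by AML status, age and baseline platelet dependence, and the RBC test by AML status, age and baseline RBC dependence.
- Define baseline dependence explicitly for each product, including the look-back window and its anchor date, for example from the 8-week transfusion history in Protocol 5.3.1.1.
- Report a risk difference stratified by the same three factors.
- Keep the two-factor CMH as a sensitivity analysis.

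The amendment summary in Protocol 1.1 describes the final analysis as completed. If the data are already unblinded, leave the ranked test as it is and report the three-factor version as a labelled supplementary analysis.

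The cost is a few lines of text and one variable that the conversion analysis already needs. The drawback is 2 × 2 × 2 = 8 strata, averaging 210/8 ≈ 26 subjects, some of them small and adding little information. In the simulations this left the test size near nominal and cost at most 0.2 power points.
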